## Design

Regular exercise is well known to have a positive effect on health [1,2]. Many of these benefits are associated with improving maximal oxygen uptake ( $\dot{V}O_{2max}$ ) [3,4]. Increasing  $\dot{V}O_{2max}$  through exercise training may improve cardiometabolic health, quality of life and increase life-expectancy [5,4].

Popular training methods aimed at improving  $\dot{V}O_{2max}$  are circuit and high intensity interval training (HIIT) and are routinely adopted by the general population, health and fitness professionals and researchers [6]. Circuit training (CT) is typically performed at a moderate or high intensity, over a period of 30-50 minutes and involves a range of aerobic, body weight and resistance exercises with minimal rest [7,8]. Low-volume HIIT is defined as 'brief, intermittent bursts of vigorous activity, interspersed by periods of rest or low intensity exercise' [9], typically prescribed at a training intensity between 80 and 100% of heart rate maximum ( $HR_{max}$ ) [10].

Whole-body CT and low volume HIIT consisting of eight to twelve one-minute interval bouts, interspersed with a similar recovery time have been shown to improve cardiometabolic health and cardiorespiratory fitness (CRF) [8,11-16]. Increases in  $\dot{V}O_{2max}$  and the anaerobic threshold (AT) have been observed following CT, however published studies are limited to sedentary and older populations, with further markers of CRF not fully explored [8,17]. Comparable improvements in  $\dot{V}O_{2max}$  and the AT have been shown following low volume HIIT, with increases in maximum oxygen pulse ( $\dot{V}O_2/HR$ ) also observed [16,18,19]. However, there is limited evidence directly comparing both training methods across a range of CRF markers, as such it is unknown which approach is most beneficial [20,21].

Direct comparisons have been made investigating low volume HIIT and moderate intensity continuous training (MICT), which is typically 30-60 minutes in duration adopting the same modality

of exercise [15,16,14]. The results demonstrate low volume HIIT to be a time efficient method, eliciting greater improvements in  $\dot{V}O_{2max}$ , although these findings are not consistently shown [22].

While HIIT and CT are feasible and effective at improving CRF, no study has directly investigated the two. Therefore, the aim of this study was to compare the effect of two weekly sessions of low volume HIIT and CT over an eight-week period on  $\dot{V}O_{2max}$  in apparently healthy middle-aged adults. We also investigated changes in other markers of CRF such as the first ventilatory anaerobic threshold ( $\dot{V}O_2$  at VAT) and maximum  $\dot{V}O_2/HR$ .

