### **Study Design**

Participants were enrolled in a randomised control trial at the University of Hull to either eight weeks of HIIT or CT (two supervised sessions per week, accompanied by an exercise physiologist). A sample size of 38 using G\*Power 3.1 software was calculated based on previously published data in which the mean difference between HIIT and MICT was  $3.2 \text{ ml}\cdot\text{kg}^{-1}\cdot\text{min}^{-1}$  with a pooled standard deviation of  $3 \text{ ml}\cdot\text{kg}^{-1}\cdot\text{min}^{-1}$  [19]. Statistical significance was set at  $\alpha = 0.05$  and power set to 0.95. To allow for 10% attrition 42 individuals were recruited to the study. To assess the effectiveness of the interventions as determined by  $\dot{V}O_{2max}$ , a maximal cardiopulmonary exercise test (CPET) to volitional exhaustion on an electronically braked cycle ergometer at baseline (visit one), and following an eight-week exercise intervention of HIIT or CT (visit two) was conducted. When attending the assessments participants were asked not to take part in any strenuous exercise 24 hours prior to the appointment, to wear suitable comfortable clothing and avoid a large meal. Visit two CPET was performed within six days of completing the exercise interventions. A thorough warm-up and cool down before and after each exercise session. All were asked to maintain their habitual physical activity patterns during the intervention. Body mass index (BMI) was calculated by dividing body weight [23] by height in meters squared and was presented as  $\text{kg}\cdot\text{m}^{-2}$ . Resting blood pressure was measured after 15 minutes of rest using a sphygmomanometer (A.C. Cossor & Son Ltd, London UK)

and stethoscope (3M Healthcare, St Paul, MN). To provide a comprehensive account of the study the Consensus on Exercise Reporting Template (CERT) was consulted [24].

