## **Participants**

Ethical approval was provided by the School of Life Sciences ethics committee at the University of Hull which was in accordance with the 1964 Helsinki declaration and its later amendments or comparable ethical standards. A total of 42 apparently healthy men and women between the age of 18-65 years were recruited to the study. Participant characteristics are given in Table 1. Enrolled individuals reported no medical history of cardiometabolic or limiting respiratory disease, were non-smokers, had a body mass index  $<30 \text{ kg m}^{-2}$ , classified as recreationally active [25] and none were taking any medication that would affect heart rate. As a condition of enrolment, those over 45 years obtained written medical clearance from a general practitioner and underwent resting and exercise 12-lead electrocardiogram (ECG) (GE Healthcare, Chalfont St Giles, United Kingdom). Written informed consent and a pre-exercise medical questionnaire was completed by all.

\*\*\*Table 1 here\*\*\*

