### **Statistical Analysis**

Statistical analysis was conducted using SPSS version 24 (IBM, New York, USA). An independent t-test was used to identify group differences at baseline. Assumptions of normality were verified using the Shapiro-Wilk test. Skewness and kurtosis of distribution was visually examined. Non-normally

distributed data was presented as median and interquartile range (IQR). A two-way (condition x time) repeated measures analysis of variance (ANOVA) was used to compare CRF pre-and post-training. Post-hoc analysis for the main effects and interactions was assessed using a Bonferroni adjustment. Group differences were compared using independent t tests. Variables were displayed as mean with 95% confidence intervals (95% CI) or standard deviation ( $\pm$ ) where specified. Partial eta squared ( $\eta_p^2$ ) effect sizes were also calculated with 0.01, 0.06 and 0.14 representing small, medium and large effect sizes, respectively [35].

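### The aim names an undefined 'middle-aged' population narrower than the 18-65 range recruited, and no planned analysis is specific to age

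*Combined protocol and SAP*

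**What the plan says.** The Design section ends with the aim: to compare two weekly sessions of HIIT or CT over eight weeks "in apparently healthy middle-aged adults". No age limits are attached to that term there or anywhere else.

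The Participants section states: "A total of 42 apparently healthy men and women between the age of 18-65 years were recruited to the study". It describes them as recreationally active and adds a condition that depends on age: "those over 45 years obtained written medical clearance from a general practitioner", together with an electrocardiogram. Actual ages are deferred to a table: "Participant characteristics are given in Table 1". In the text available, that table is only a placeholder.

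The Statistical Analysis section gives the main model: "A two-way (condition x time) repeated measures analysis of variance (ANOVA) was used to compare CRF pre-and post-training". Independent t tests are used for group differences. Age does not appear in any analysis.

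**The concern.** The population is part of the objective, because it fixes the people to whom the conclusion applies. Here the objective names one population and the recruitment statement describes a wider one. The clearance step for those over 45 shows that enrolment at 45 or younger was provided for, so the wider range was intended.

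A conclusion worded to match the aim would credit middle-aged adults with an effect averaged over everyone enrolled between 18 and 65. A reader could not tell from the plan which ages 'middle-aged' covers, and nothing in the analysis would produce an estimate for that group.

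**Working it through.** **1. The plan's own figure.** The only design figure is the sample size: "A sample size of 38 using G\*Power 3.1 software was calculated". The Study Design section gives a difference of 3.2 and a pooled SD of 3 (ml/kg/min), alpha 0.05 and power 0.95. Sidedness is not stated, and I assume equal allocation.

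- d = 3.2/3 = 1.067.
- One-sided: 20 per arm, 40 in total, by the normal approximation and by the t test. This is close to 38.
- Two-sided: 23 per arm (46) by the normal approximation, 24 per arm (48) by the t test.
- Attrition: 38 × 1.1 = 41.8, so 42.

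Sidedness is a separate matter. What counts here is that no input involves age, so the calculation does not show which population was meant.

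**2. The statements side by side.**

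| Element | Section | Content |
|---|---|---|
| Target population | Design | Middle-aged adults, undefined |
| Recruited population | Participants | Adults aged 18-65, recreationally active |
| Age-dependent rule | Participants | Extra clearance above 45 only |
| Analysis | Statistical Analysis | Condition by time; no age term |
| Actual ages | Table 1 | Not in the text |

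On any ordinary meaning of the term, the first row is a subset of the second, and the fourth row does not isolate it.

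**3. What the analysis estimates.** With two visits, the condition-by-time term is the difference between arms in mean change. Let π be the middle-aged share of those analysed, the same in both arms in expectation under randomisation. Then

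Δ(all) = π × Δ(middle-aged) + (1 − π) × Δ(other ages).

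Reading Δ(all) as the middle-aged effect is therefore wrong by

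Δ(all) − Δ(middle-aged) = (1 − π) × [Δ(other ages) − Δ(middle-aged)].

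This is zero if everyone is middle-aged (π = 1) or if the HIIT-CT difference does not vary with age. As π falls towards 0 it approaches the whole difference in effect between the age groups. The documents give neither π nor that difference, so no value can be put on the error.

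**4. Precision of the planned comparison.** Assume the same SD σ at both visits, correlation ρ between visits, and n per arm.

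- Change-score comparison: variance (2/n) × 2σ²(1 − ρ).
- Post-training value adjusted for baseline: variance (2/n) × σ²(1 − ρ²).
- Ratio, adjusted to change score: (1 + ρ)/2.

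ρ is not in the documents. For assumed values of 0.5, 0.7 and 0.9 the variance ratio is 0.75, 0.85 and 0.95, and the standard error ratio (its square root) is about 0.87, 0.92 and 0.97. This ignores the small loss of degrees of freedom. The further gain from age cannot be computed. Adjustment still returns one average over ages 18-65, so it does not settle step 3.

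**The case against.** The strongest reply is that this is a matter of a few words. The range 18-65 contains middle-aged adults, the term may describe the typical age of the sample rather than an eligibility limit, and Table 1 may show a largely middle-aged group. The over-45 rule provides for older participants as much as younger ones and says nothing about proportions. An average over all ages misleads about the middle-aged only if the effect varies with age, and the documents give no evidence that it does. All of this stands, and it limits the point to applicability. It does not remove the mismatch: even a middle-aged mean in Table 1 would leave the aim and the recruitment statement naming different populations.

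Three stronger readings are tempting and should not be drawn.

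- A reader might infer that the trial as enrolled does not answer its question. The documents do not show who was enrolled, so this is not established.
- A reader might size the problem by counting eligible years: ages 18-39 are 22 of 48, or 46%, if middle age starts at 40. That counts calendar years, not participants. It would approximate the sample only if ages were evenly spread, which nothing in the documents supports.
- The Design section says that CT studies are confined to sedentary and older people, so a reader might infer that age is the gap the trial fills. The gap that leads to the aim is the lack of a direct comparison of the two methods.

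It is also fair to object that age adjustment does not yield an effect in middle-aged adults. That is correct. The adjustment is recommended for precision only.

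**Conclusion.** The point holds as a mismatch of scope. The aim's population is undefined and narrower than the one recruited, and no analysis is specific to age. What the trial estimates is an average HIIT-CT difference in recreationally active adults aged 18-65. Its applicability to middle-aged adults turns on the enrolled age distribution and on whether the effect varies with age, and neither is known from the documents. The absence of Table 1 from this text is not a fault in the plan.

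The randomised comparison, its error rate and its power are untouched. The consequence is confined to the wording of the conclusion, and no participant count can be attached to it. The precision gain from adjustment rests on equal variances at the two visits and an unknown correlation, with a standard error about 3% to 13% lower over the assumed range of 0.5 to 0.9.

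**What to change.** **Aim and conclusion.** In the last paragraph of the Design section, and in the conclusion drawn from it, replace 'middle-aged adults' with 'recreationally active adults aged 18-65 years'. Report the age distribution by arm; if Table 1 already does so, nothing further is needed. Do not add a lower age limit to the Participants section. Recruitment is described as complete, and a limit written in afterwards could misstate who was enrolled.

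**Analysis (separate change).** In the Statistical Analysis section, estimate the HIIT-CT difference in post-training maximal oxygen uptake with a 95% confidence interval, adjusted for baseline maximal oxygen uptake and age. Baseline is measured at visit one. Age is needed for the recruitment range, the over-45 rule and the age-predicted heart rate criterion, so both are already collected. State that the result is an average over ages 18-65.

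**Cost.** A short wording change and one regression model with two covariates, with no new data. The downside is a less specific population claim.

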### **Study Design**

Participants were enrolled in a randomised control trial at the University of Hull to either eight weeks of HIIT or CT (two supervised sessions per week, accompanied by an exercise physiologist). A sample size of 38 using G\*Power 3.1 software was calculated based on previously published data in which the mean difference between HIIT and MICT was  $3.2 \text{ ml}\cdot\text{kg}^{-1}\cdot\text{min}^{-1}$  with a pooled standard deviation of  $3 \text{ ml}\cdot\text{kg}^{-1}\cdot\text{min}^{-1}$  [19]. Statistical significance was set at  $\alpha = 0.05$  and power set to 0.95. To allow for 10% attrition 42 individuals were recruited to the study. To assess the effectiveness of the interventions as determined by  $\dot{V}O_{2max}$ , a maximal cardiopulmonary exercise test (CPET) to volitional exhaustion on an electronically braked cycle ergometer at baseline (visit one), and following an eight-week exercise intervention of HIIT or CT (visit two) was conducted. When attending the assessments participants were asked not to take part in any strenuous exercise 24 hours prior to the appointment, to wear suitable comfortable clothing and avoid a large meal. Visit two CPET was performed within six days of completing the exercise interventions. A thorough warm-up and cool down before and after each exercise session. All were asked to maintain their habitual physical activity patterns during the intervention. Body mass index (BMI) was calculated by dividing body weight [23] by height in meters squared and was presented as  $\text{kg}\cdot\text{m}^{-2}$ . Resting blood pressure was measured after 15 minutes of rest using a sphygmomanometer (A.C. Cossor & Son Ltd, London UK)

and stethoscope (3M Healthcare, St Paul, MN). To provide a comprehensive account of the study the Consensus on Exercise Reporting Template (CERT) was consulted [24].

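### The printed inputs (difference 3.2, SD 3, alpha 0.05) give about 0.89 power at 38 for a two-sided HIIT versus CT comparison, not the stated 0.95, unless an unstated input was used

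*Combined protocol and SAP*

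**What the plan says.** The sample-size text is in Study Design. It gives the result first, "A sample size of 38 using" G*Power 3.1, then the source: earlier data "in which the mean difference between HIIT and MICT was" 3.2 ml/kg/min "with a pooled standard deviation of" 3 ml/kg/min. Alpha is 0.05 "and power set to 0.95. To allow for 10% attrition 42 individuals were recruited to the study".

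VO2max is measured twice, "at baseline (visit one), and following an eight-week exercise intervention of HIIT or CT (visit two) was conducted". The aim, at the end of the Design section, is "to compare the effect of two weekly sessions of low volume HIIT and CT over an eight-week period" on VO2max. The main analysis in Statistical Analysis is this: "A two-way (condition x time) repeated measures analysis of variance (ANOVA) was used to compare CRF pre-and post-training". That section also provides for Bonferroni-adjusted post-hoc work on main effects and interactions, and for independent t tests of group differences.

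The documents do not state the G*Power test family, the sidedness, the allocation ratio, a pre-post correlation, or whether SD 3 describes change or values at one visit.

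**The concern.** The aim asks whether VO2max changes more under one programme than under the other. In a two-group, two-visit design the condition x time interaction answers that question, and its F test is identical to a two-sided t test comparing mean change between groups. The standardised difference from the printed inputs is 3.2/3 = 1.067. In a two-sided test, 38 participants do not give that difference 0.95 power.

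A reader will take 0.95 as the chance of detecting 3.2 ml/kg/min on the comparison of interest, and will read a null result accordingly. If SD 3 is the SD of change, the chance of missing that difference is about 11% at 38, or 8% at 42, rather than 5%.

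**Working it through.** **Inputs.** From Study Design: difference 3.2, SD 3, alpha 0.05, 38 evaluable, 42 recruited. Assumed: 1:1 allocation (unequal allocation would lower power). Inferred: two-sided, because the planned F test has no direction and no one-sided test is mentioned.

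**1. Reproducing 38.**
- *Between-group main effect in a repeated-measures ANOVA.* Let f = 1.067/2 = 0.533, with m = 2 visits and an assumed correlation of 0.5. The noncentrality is lambda = f² × N × m / (1 + (m − 1) × rho). At N = 38, lambda = 0.2844 × 38 × 2 / 1.5 = 14.41 and power is 0.958. At N = 36, lambda = 13.65 and power is 0.948. The smallest even N is therefore 38.
- *One-sided t test.* Power is 0.943 at 38 and 0.952 at 40. This is close, but it gives 40.

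**2. Two-sided comparison with SD 3.** The noncentrality is (3.2/3) × √(N/4), on N − 2 degrees of freedom.

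| N | Noncentrality | Critical t | Power |
|---|---|---|---|
| 38 | 3.288 | 2.028 | 0.892 |
| 40 | 3.373 | 2.024 | 0.908 |
| 42 | 3.456 | 2.021 | 0.921 |
| 46 | 3.617 | 2.015 | 0.943 |
| 48 | 3.695 | 2.013 | 0.951 |

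The table applies to the interaction if SD 3 is the SD of change, and to an independent t test in which SD 3 is the SD of the compared values. With SD 3, the smallest difference detectable with 0.95 power is 3.61 at 38 and 3.42 at 42.

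**3. Whether the main-effect result carries over.** With a single-visit SD of 3 and correlation rho, the SD of change is 3 × √(2(1 − rho)). At rho = 0.5 this is 3.0, so the inputs that return 38 for the main effect give the interaction power of 0.892. The main effect also averages over visits. If the 3.2 appears only after training, the averaged difference is 1.6 and the main effect has power of 0.455 at 38.

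**4. When 0.95 does hold at 38 for the interaction.**
- *SD of change:* solving for two-sided power of 0.95 gives 2.66 at 38 (2.81 at 42). A value of 2.66 would print as 3.
- *Single-visit SD of 3, rho assumed:*

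| rho | SD of change | Power at 38 |
|---|---|---|
| 0.4 | 3.29 | 0.832 |
| 0.5 | 3.00 | 0.892 |
| 0.61 | 2.65 | 0.952 |
| 0.7 | 2.32 | 0.985 |
| 0.8 | 1.90 | 0.999 |

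**5. Precision.** The expected 95% CI half-width for the difference in change is t(0.975, N − 2) × 3 × √(4/N), again with SD of change 3. It is 1.97 at 38 and 1.87 at 42.

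**The case against.** The strongest reply is that no arithmetic error has been shown. A standard G*Power option returns exactly 38, and the SD is printed as a whole number. An SD of change anywhere from 2.5 to 3.5 would appear as 3, and across that range power at 38 runs from about 0.97 down to about 0.78. An unrounded value of about 2.59 to 2.66 would make 38 the smallest even number giving 0.95 for the interaction itself. Whether SD 3 describes change or single-visit values depends on a cited study that the documents do not reproduce. Statistical Analysis also covers main effects and independent t tests, and no single primary contrast is named.

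Most of this stands. It means that 0.95 is not excluded, and that main effects and t tests cannot be dismissed as unplanned. It does not restore the stated figure. An independent two-sided t test with SD 3 also has power of only 0.892 at 38, and the main-effect route that returns 38 implies 0.892 for the contrast answering the aim. Rounding could equally hide a power below 0.89.

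Three stronger readings are tempting and are not supported:
- *That 38 is wrong.* The unstated inputs could justify it.
- *That a one-sided test was used.* The documents do not say so, and that test would give 40.
- *That 0.95 is necessarily too high.* With a single-visit SD of 3 and a correlation of 0.7, power would be 0.985.

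It is also fair to say that the consequence is small: recruitment is described as complete, and confidence intervals are among the planned summaries.

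**Conclusion.** As printed, the inputs do not give the stated 0.95 at 38 for a two-sided HIIT versus CT comparison. They give about 0.89 at 38 and 0.92 at 42, with 48 needed for 0.95. This rests on 1:1 allocation, a two-sided test, and SD 3 at face value as the SD of change (or the SD used in an independent t test). Reaching 0.95 at 38 on the condition x time contrast takes an input that the documents do not state: an SD of change of about 2.66 or less, or a single-visit SD of 3 with a pre-post correlation of about 0.61 or more.

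A reader might infer that the trial is underpowered. The documents do not support that, since power stays near 0.9 on the face-value reading. The point concerns the stated figure only. Severity is minor, and confidence is medium because the meaning of SD 3 is not given.

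**What to change.** Revise the sample-size text in Study Design, with no change to enrolment or analysis.

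1. State the calculation actually done: the G*Power test, its sidedness, what SD 3 measures, and any correlation entered.
2. Restate the power for the two-sided condition x time contrast.
   - If SD 3 is the SD of change: *For the condition x time contrast, 38 evaluable participants give about 89% power, and 42 about 92%, to detect a 3.2 ml/kg/min difference in change at two-sided alpha 0.05.*
   - Otherwise: give the power at the unrounded SD of change or the pre-post correlation actually used, and state that value. For a single-visit SD of 3 at 38 participants, examples are 89% at a correlation of 0.5, 95% at about 0.61 and 98.5% at 0.7.

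The cost is one or two sentences. The downside is that the stated power may fall by about 3 points (0.95 to 0.92 at 42) to 6 points (0.95 to 0.89 at 38). If the inputs used do support 0.95, the same sentences will show it.
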